Consequently, invasive wire-based solutions for physiological assessment were developed to identify ischemia-producing epicardial coronary stenoses [3, 8]. Current European guidelines emphasize the importance of performing physiological assessment for all intermediate coronary artery stenoses, including left main stenosis, side branch stenosis and serial stenoses, when functional information from non-invasive tests is lacking [9]. Moreover, in patients with multivessel CAD, PCI guided by fractional flow reserve (FFR) results in an improved outcome irrespective of available non-invasive functional test results [9]. The development of FFR and its use in guiding percutaneous intervention, has led to improved patient outcomes compared with angiography guidance alone [10]. New developments in wire-free functional coronary assessment derived from the angiogram, globally termed as functional coronary angiography (FCA), may contribute to a more widespread use of physiology to diagnose the cause of ischemia and to plan and guide coronary revascularization [11–16]. These systems are based on vessel lumen reconstructions from coronary angiography, with the aim of providing FFR-like estimates of stenosis severity, whilst not requiring pharmacological agents or intracoronary instrumentation. Different software approaches to FFR estimation derived from coronary angiography have been developed. Several studies demonstrated the good correlation between wire-based and Angiography-derived FFR with a cut-off of 0.80. In a recent meta-analysis of 16 studies, 819 patients and 969 vessels with paired FFR and Angiography-derived FFR were included. Authors found an overall satisfactory agreement (mean difference 0.009 ± 0.068 , $I^2 = 39.6$) of angiography- and wire- derived FFR. The diagnostic performance was sensitivity 84% (95%CI: 77-90, $I^2 = 70.1$), specificity 88% (95%CI: 84-91, $I^2 = 60.1$); positive predictive value 80% (95%CI: 76-85, $I^2 = 33.4$), and negative predictive value 95% (95%CI: 93-96, $I^2 = 75.9$) [15]. Several non-inferiority trials are ongoing to provide the data answer regarding Angiography-derived FFR clinical equivalence in comparison with wire-based FFR

(Tab.I). Angiography-derived FFR analyzability depends on quality of angiography, and it is feasible in around 80% of the cases.

The Vulnerable Plaque: Pathophysiology of Coronary Artery Disease Progression

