6. DESCRIPTION OF THE DISEASE IN THE STUDY

Ischemic Heart Disease and General Information on Coronary Angiography

The selection of eligible patients is based on the review of hospital registries and the analysis of coronary angiography procedures performed from January 2010 to December 2024.

Participants with suspected CAD undergo coronary angiography as part of the standard diagnostic and therapeutic pathway, in accordance with current guidelines for the management of ischemic heart disease. A patient is considered eligible if at least one mild or intermediate coronary stenosis is identified on angiographic assessment and subsequently evaluated with a coronary physiology test (fractional flow reserve [FFR] or angiography-derived FFR). These functional assessments guide the operator's decision to proceed with or defer vessel revascularization.

If a physiological evaluation of CAD is performed, the corresponding data — including FFR and/or angiography-derived FFR — are collected and recorded. The initial angiogram of all patients will be stored, anonymized, and kept locally for functional analysis (acceptable formats include CD, DVD, or digital files).

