7. ENDPOINTS

Primary Endpoint

The primary endpoint is the composite risk of vessel-oriented composite endpoint (VOCE), including target vessel revascularization (TVR), vessel-related myocardial infarction (MI), and cardiovascular death.

Secondary Endpoint

- Individual components of the primary endpoint.
- Hospitalization for unstable angina.
- Angina status assessed using the Seattle Angina Questionnaire (SAQ). The SAQ will be used to evaluate patients' quality of life and the impact of angina symptoms over time. Scores from the main subscales (physical limitation, angina stability, angina frequency, treatment perception, and overall quality of life) will be analysed to correlate symptom severity with coronary physiology parameters (e.g., FFR/angiography-derived FFR).
- Number of prescribed antianginal drugs. The number of prescribed antianginal medications will be monitored to assess the intensity of pharmacological treatment required during follow-up. This parameter will serve as a proxy for residual disease severity and will allow comparison between patients managed conservatively and those treated with invasive interventions.

[figure not shown]

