15. DEFINITIONS

Ischemia-driven target vessel revascularization (TVR)

All ischemia-driven revascularizations refer to the target lesion that led to enrollment into the study.

Requires the following criteria:

- Ischemic symptoms consistent with CCS class ≥ 3 angina despite optimal medical therapy

AND

- PCI or CABG of either the target that led to enrollment into the study PLUS at least ONE of the following:
 - Positive functional study (Exercise or myocardial perfusion imaging or stress or dobutamine echo) demonstrating clear evidence of reversible ischemia corresponding to a stenosis in the target vessel;
 - New ischemic ECG changes (ST-segment depression ≥ 1 mm, ST-segment elevation ≥ 1 mm or T wave inversion ≥ 2 mm) at rest or with exertion in a distribution consistent with a stenosis in the target vessel;
 - FFR ≤ 0.80 , iFR ≤ 0.89 , cFFR ≤ 0.85 , Angiography-derived FFR ≤ 0.80 in the target vessel.

Vessel-related myocardial infarction (MI)

MI is defined according to the 4th universal definition of myocardial infarction. The leading symptom that initiates the diagnostic and therapeutic cascade in patients with suspected MI is chest pain. Based on the electrocardiogram (ECG), two groups of patients should be differentiated: Patients with acute chest pain and persistent (>20 min) ST-segment elevation. This condition is termed ST-elevation ACS and generally reflects an acute total coronary occlusion. Most patients will ultimately develop an ST-elevation myocardial infarction (STEMI). The mainstay of treatment in these patients is immediate reperfusion by primary angioplasty or fibrinolytic therapy.

Patients with acute chest pain but no persistent ST-segment elevation. ECG changes may include transient ST-segment elevation, persistent or transient ST-segment depression, T-wave inversion, flat T waves or pseudo-normalization of T waves or the ECG may be normal. The clinical spectrum of NSTEMI may range from patients free of symptoms at presentation to individuals with ongoing ischemia, electrical or hemodynamic instability or cardiac arrest.

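### The TVR definition has no angiographic-severity item, so whether a non-MI target-vessel revascularisation counts depends on whether an ischaemia test was recorded

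*Protocol*

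**What the plan says.** Section 7 defines the primary endpoint, VOCE, as a composite "including target vessel revascularization (TVR), vessel-related myocardial infarction (MI), and cardiovascular death". The only definition of TVR is in Section 15, under the ischaemia-driven heading. It has two parts joined by AND:

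- a symptom condition: "Ischemic symptoms consistent with CCS class ≥ 3 angina despite optimal medical therapy";
- the procedure plus evidence: "PCI or CABG of either the target that led to enrollment into the study PLUS at least ONE of the following".

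The evidence list has three items: a positive stress or perfusion study pointing to the target vessel; new ST or T-wave changes "at rest or with exertion in a distribution consistent with a stenosis in the target vessel"; and a physiology index at or below its cut-off (FFR, iFR, cFFR, or "Angiography-derived FFR ≤ 0.80 in the target vessel"). Neither percent diameter stenosis nor occlusion appears.

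Other sections bear on how often the items will be available. The Introduction reports that guidelines stress "the importance of performing physiological assessment for all intermediate coronary artery stenoses" when non-invasive functional information is lacking. Section 6 states that "The initial angiogram of all patients will be stored, anonymized, and kept locally for functional analysis", and the synopsis has the investigators analyse the index angiogram. Section 8 collects follow-up from records, visits and telephone calls. Index procedures run from January 2010 to December 2024.

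**The concern.** Consider a patient with class 3 angina whose target vessel is found severely narrowed or occluded at a repeat angiogram and is revascularised on that finding, with no stress test, ECG change or physiology value on file. The symptom and procedure conditions are met, but the case is not a TVR event. Physiology is recommended mainly for intermediate stenoses, so a severe lesion is one in which the operator may well not have measured it.

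At stake is the ascertainment of a primary-endpoint component. Two patients with the same clinical course can be classified differently because one had a test on file. Testing practice may differ between operators and calendar years; the Introduction itself presents angiography-derived FFR as a new development. Section 11 justifies the sample size by the number of evaluable events, so uncounted events also cost information.

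**Working it through.** **1. Logic of the definition.** TVR event = (class 3 or worse angina) AND (PCI or CABG of the target) AND (functional study OR ECG change OR physiology index). If all three evidence items are absent, the result is no event, whatever the angiogram shows.

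**2. Can the missing evidence be supplied later?**

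- *Functional study and ECG change.* For an event already past, only what was recorded then is available. For later events the protocol schedules no such test.
- *Physiology index.* A wire-based value must have been measured at the procedure. Angiography-derived FFR could in principle be computed later from the repeat angiogram. The protocol does not forbid this, but states functional analysis only for the index angiogram and puts feasibility at around 80%.
- *Other components.* A presentation that meets the MI definition still enters VOCE as MI, and an MI with no identifiable culprit is counted as target-vessel related.

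The uncounted group is therefore revascularisation for class 3 or worse angina, without MI and with none of the three items on file.

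**3. Effect on the association.** The protocol gives no figure for the share of revascularisations without a listed test, so there is nothing to reproduce. As an illustration, assume 10-year risks of 16% TVR-only and 10% MI or death in low-FFR vessels, 7% and 7% in high-FFR vessels, and groups of equal size. With q the share of TVR lacking a listed test:

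ratio = [16(1 − q_low) + 10] / [7(1 − q_high) + 7]

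loss = (16·q_low + 7·q_high) / (26 + 14)

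| q_low | q_high | Ratio | VOCE events lost |
|---|---|---|---|
| 0 | 0 | 26.0/14.0 = 1.86 | 0 |
| 20% | 20% | 22.8/12.6 = 1.81 | 4.6/40 = 11.5% |
| 40% | 20% | 19.6/12.6 = 1.56 | 7.8/40 = 19.5% |
| 50% | 20% | 18.0/12.6 = 1.43 | 9.4/40 = 23.5% |
| 20% | 40% | 22.8/11.2 = 2.04 | 6.0/40 = 15.0% |

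The last row swaps the shares of the third, and the ratio moves away from the null. The direction follows from the assumed shares.

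**4. Effect on information.** Section 11 cites 12-month composite rates of 6.1% to 6.7% and plans 1000 to 1200 patients: 1000 × 0.061 = 61 to 1200 × 0.067 = 80 events. It states no effect size, so its 80% power cannot be re-derived. Assume a 50:50 split, two-sided alpha 0.05 and a hazard ratio of 2.0. Power = Φ(ln 2 · √(D/4) − 1.96), with D the number of events:

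| Assumed share of events uncounted | Events | Power |
|---|---|---|
| 0 | 61–80 | 77–87% |
| 10% | 55–72 | 73–84% |
| 20% | 49–64 | 68–79% |
| 30% | 43–56 | 62–74% |

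The primary analysis uses all follow-up to database lock, so actual counts will differ.

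**The case against.** The strongest reply is that the omission is deliberate and coherent. The endpoint is called ischaemia-driven, and the Introduction argues that anatomy alone does not show haemodynamic significance. Requiring functional proof contradicts nothing in the protocol. That stands: this is a risk of under-ascertainment, not an internal contradiction. But the argument is strongest for intermediate lesions. It explains less well why a severe or occluded vessel with class 3 angina should go uncounted, when Section 15 resolves uncertain MIs and deaths towards inclusion.

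A second reply is that the residue is narrow. One item suffices, patients with severe angina and a critical lesion may often have ECG changes or a positive stress test, and MI cases count anyway. This also stands, and limits the size of the problem to an unknown degree.

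A third is that the adjudication charter, which is not shown, may deal with the case. It may, but it cannot be assumed to override an explicit list in the protocol.

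A reader might go further than the documents allow in three ways:

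- *That the rule biases the FFR–VOCE association towards the null.* This needs low-FFR vessels to lose proportionately more events. Index physiology guided revascularisation (Sections 6 and 8), so many low-FFR vessels were presumably treated, and the pattern of loss is unknown.
- *That later angiography-derived FFR is ruled out.* Section 6 says the initial angiogram is kept; it does not say that it is the only one. Nor do the documents say whether an occluded vessel can be analysed.
- *That 70% diameter stenosis is the protocol's own threshold.* The Introduction uses it only in describing a cited trial.

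**Conclusion.** The point holds as test-dependent under-ascertainment of one primary-endpoint component. It rests on Section 15 governing TVR in the primary endpoint. That is the only definition given, although the synopsis and Section 7 name TVR without the ischaemia-driven qualifier. Wherever a non-MI revascularisation for class 3 or worse angina was done on the angiogram alone, the event is lost.

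How many such cases there are, and which way they move the association, cannot be determined from the documents. The ratios of 1.43 to 2.04 and the power figures are illustrations under stated assumptions, not estimates for this study. The change is worth making before adjudication because it is cheap and removes a dependence on testing practice.

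**What to change.** Add a fourth qualifying item to the evidence list in Section 15 and to the adjudication charter: severe stenosis or occlusion of the target vessel, judged by the blinded committee from the angiogram or report of the repeat procedure. The sponsor should pre-specify and justify the severity threshold. Report TVR and VOCE both with and without this item. If angiographic severity was left out on purpose, say so and give the reason. In either case, align the TVR wording in the synopsis and Section 7 with Section 15.

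The cost is one line in Section 15, one in the charter, and a second tabulation of TVR and VOCE. The item uses material that the repeat procedure itself generates. The drawback is that it rests on a stenosis reading and is less specific for ischaemia; reporting both versions keeps the physiology-based definition visible. The change concerns endpoint classification only and does not touch care.

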4. STUDY OBJECTIVES

Primary Objective

The primary objective is to identify a risk profile for vessel-oriented composite endpoint (VOCE) associated with the functional characteristics of coronary lesions documented during coronary angiography.

Secondary Objectives

Secondary objectives include:

- Assessing the prognostic value of physiological parameters (invasive FFR and angiography-derived FFR).
- Analysing the clinical, demographic, and angiographic characteristics of patients with coronary lesions evaluated by coronary physiology to identify high-risk subgroups.
- Investigating the correlation between coronary physiology values and angina symptoms.
- Comparing invasive FFR with angiography-derived FFR.
- Comparing clinical outcomes between patients managed conservatively and those undergoing invasive interventions.

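### Section 15 lets an FFR of 0.80 or below, with no change from index required, be the only objective evidence for a TVR, so in deferred vessels event counting can depend on the exposure itself

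*Protocol*

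**What the plan says.** - **Exposure.** Protocol Section 4 sets the primary objective to "identify a risk profile for vessel-oriented composite endpoint (VOCE) associated with the functional characteristics of coronary lesions". A secondary objective is "Assessing the prognostic value of physiological parameters (invasive FFR and angiography-derived FFR").
- **Outcome.** VOCE combines TVR, target-vessel MI and cardiovascular death. The Synopsis and Section 7 list TVR without qualification. The only TVR definition, in Section 15, is for ischemia-driven TVR.
- **Qualifying rule.** Section 15 requires "Ischemic symptoms consistent with CCS class ≥ 3 angina despite optimal medical therapy", and PCI or CABG of the target, "PLUS at least ONE of the following": a positive functional study, new ischemic ECG changes, or "FFR ≤ 0.80 , iFR ≤ 0.89 , cFFR ≤ 0.85 , Angiography-derived FFR ≤ 0.80 in the target vessel". It sets no time for the physiology value, no minimum change from index and no requirement to use the index method.
- **Index management.** Section 6 says "These functional assessments guide the operator's decision to proceed with or defer vessel revascularization".
- **Measurement scatter.** For angiography-derived against wire-based FFR, the Introduction reports "Authors found an overall satisfactory agreement (mean difference 0.009", with a standard deviation of 0.068. It mentions 0.80 as the cut-off used in earlier studies. No section fixes 0.80 as the index threshold for this registry.

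**The concern.** The exposure variable is also one of three interchangeable evidence items inside a component of the primary endpoint. Take two deferred vessels that have not changed since index, in patients with the same angina and the same decision to revascularise, and with no stress test or ECG finding. The vessel with index FFR just above 0.80 can meet the physiology item through measurement scatter or a switch of method. The vessel at 0.92 rarely can. Whether the event is counted then depends on the exposure even if index FFR has no bearing on who returns with symptoms.

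Blinded adjudication does not help, because the committee would be applying the rule correctly. Adjustment in the Cox model of Section 12 does not help either, because the dependence lies in how the outcome is defined. At stake is how much of an observed FFR-VOCE association is prognosis and how much is the counting rule. Section 13 cites objective endpoint criteria as protection against bias and does not mention this overlap.

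**Working it through.** The protocol gives no figure for this effect, so there is none to reproduce. The calculation asks what the rule alone produces when symptomatic revascularisation is unrelated to index FFR and the vessel has not changed.

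**Inputs**
- Threshold 0.80 (Section 15).
- Switch of method: mean difference b = +0.009 or -0.009, s = 0.068 (Introduction). This is a between-method figure, used as a proxy for index-to-repeat scatter.
- Same method: b = 0, s = 0.02 to 0.04 (assumed).
- q, the share of symptomatic revascularisations with a qualifying stress test or ECG item: 0.5, varied to 0.2 and 0.8 (assumed).
- m, the share with a physiology value at the later procedure: 1, varied to 0.5 (assumed).
- w, the TVR share of VOCE in the comparison group at 0.92: 0.3 to 0.7 (assumed).

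**Formulas**
- Chance that the later value is 0.80 or below, given index f: P(f) = Φ((0.80 − f − b)/s).
- Chance that the procedure is counted: C(f) = q + (1 − q) × m × P(f).
- Counted-TVR ratio: R = C(0.82)/C(0.92).
- Ratio in VOCE: 1 + w × (R − 1), since MI and cardiovascular death do not use the item.

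**Results with q = 0.5, m = 1**

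| Case | P(0.82) | P(0.92) | R |
|---|---|---|---|
| Switch, b = +0.009 | 33.5% | 2.9% | 0.6674/0.5145 = 1.30 |
| Switch, b = −0.009 | 43.6% | 5.1% | 0.7179/0.5257 = 1.37 |
| Same method, s = 0.02 | 15.9% | 0.0% | 0.5793/0.5000 = 1.16 |
| Same method, s = 0.04 | 30.9% | 0.1% | 0.6543/0.5007 = 1.31 |

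So R is 1.16-1.37. In VOCE the lower end is 1 + 0.3 × 0.16 = 1.05 and the upper end 1 + 0.7 × 0.37 = 1.26.

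**Sensitivity**
- m = 0.5 (half have a later physiology value): R = 1.08-1.19. VOCE runs from 1 + 0.3 × 0.08 = 1.02 to 1 + 0.7 × 0.19 = 1.13.
- q = 0.8, m = 1: R = 1.04-1.09.
- q = 0.2, m = 1: R = 1.6-2.3.
- Physiology item not used, either because every symptomatic procedure counts or because only the ECG and stress-test items qualify: C is the same at every f, so R = 1.00.

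**Treated vessels.** Suppose a low-FFR vessel was treated at index and now reads about 0.90 (assumed). Compare it with a deferred vessel at 0.82. With s = 0.068 and no drift, P(0.90) = 7.1% and P(0.82) = 38.4%, so at q = 0.5 the ratio is (0.5 + 0.5 × 0.071)/(0.5 + 0.5 × 0.384) = 0.77. Over s = 0.03-0.068 and a downward drift of 0-0.03 (assumed), it is 0.62-0.80. Here the group with the lower index FFR has fewer counted events.

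**The case against.** **Symptoms and a procedure are mandatory.** A reader might infer that an FFR value alone can make a TVR. It cannot: the angina criterion and PCI or CABG are both required. The value replaces only the stress-test or ECG evidence. The calculation already conditions on symptoms and a procedure.

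**Section 15 may not govern the primary endpoint.** If VOCE counts any TVR, as the Synopsis and Section 7 literally read, the item does not decide what enters VOCE. This stands. The point is conditional until the passages are reconciled. Against it, Section 15 holds the only TVR definition, and Section 13 says events are adjudicated on predefined definitions.

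**Direction.** A reader might infer a bias that always favours a low-FFR, high-VOCE result. Section 4 states no directional hypothesis, and index physiology guided treatment, so the effect can reverse between treated and deferred vessels.

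**Low FFR is meant to qualify.** A deferred vessel that stays at 0.75 meets the protocol's own physiological criterion, so comparing it with 0.90 would mix the counting rule with the relation under study. That is accepted, and the illustration uses 0.82 against 0.92.

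**Timing and cut-off.** Section 15 does not say that the value must be a repeat, and 0.80 is not stated as an index rule. Neither is needed: a fixed threshold on the exposure scale is enough to produce the gradient.

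**Scope.** Companion analyses often sit in an SAP and adjudication rules in the committee charter, and neither is at hand. Their content is not claimed to be missing. The point concerns the rule that the protocol itself fixes.

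**Conclusion.** The concern holds in a limited form. If Section 15 governs the TVR component of VOCE, then among vessels deferred at index the counting of an identical symptomatic revascularisation depends on index FFR, and a definition-induced part enters the FFR-VOCE association. Whether that condition is met cannot be settled from the protocol as written.

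The size is modest in the central illustration and sensitive to its assumptions. The ratios are not estimates for this registry: the share with other evidence, the share with a later physiology value, the same-method scatter and the TVR share are all assumed, and 0.068 is a between-method proxy. The effect shrinks towards none as stress-test or ECG evidence becomes more common or later physiology less often measured.

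The documents do not support the stronger conclusion that any observed FFR-VOCE association is an artefact.

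**What to change.** 1. Reconcile the Synopsis and Section 7 with Section 15 on which TVR counts in VOCE.
2. Record at adjudication which evidence item or items qualified each TVR. Keep the committee blinded to index physiology, as Section 3 intends. Asking it to compare the qualifying value with the index method or value would reveal the exposure, so make any such comparison in the analysis.
3. In Section 12, add a companion Cox analysis of FFR and VOCE, in deferred vessels and overall, in which TVR counting does not depend on the physiology item. Do it once with all symptomatic target-vessel revascularisations and once with only those qualifying by ECG or functional study. Report both beside the primary result.

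The cost is one adjudication field and a small set of additional models, with no extra patients or procedures. Once item 1 is settled, the reported endpoint stays as it is. The field is cheapest to add before adjudication, since adding it later means reviewing events again.

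The downside is that the first companion version admits some revascularisations without objective ischaemia, and the second loses some events. Neither removes the dependence that arises when operators use FFR to decide on later procedures. The companion result should therefore qualify a prognostic claim and not be its sole basis.
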